13.5 Preexisting Condition

A preexisting condition is one that is present at the start of the study. A preexisting condition should be recorded as an adverse event if the frequency, intensity, or the character of the condition worsens during the study period.

13.6 General Physical Examination Findings

At screening, any clinically significant abnormality should be recorded as a preexisting condition. At the end of the study, any new clinically significant findings/abnormalities that meet the definition of an adverse event must also be recorded and documented as an adverse event.

13.7 Post-study Adverse Event

All unresolved adverse events should be followed by the sponsor-investigator until the events are resolved, the subject is lost to follow-up, or the adverse event is otherwise explained. At the last scheduled visit, the sponsor-investigator should instruct each subject to report, to the sponsor-investigator, any subsequent event(s) that the subject, or the subject's personal physician, believes might reasonably be related to participation in this study.

13.8 Patients on Anticoagulants and Antiplatelets

Patients on warfarin will hold their medication prior to procedure or reduce their dose as directed by their primary provider. They will then have an INR checked on evaluation. Patients with an INR less than 1.4 will undergo CS Reducer implantation and invasive coronary reactivity testing. Those with an INR >1.4, will be asked to hold their warfarin for additional time until the INR is less than 1.4, and then the procedure will be undertaken.

Novel anticoagulant medications will be held 3-5 days prior to procedure as mandated by laboratory protocol.

While antiplatelet therapy may increase the bleeding risk, it will not preclude enrollment in the study. Given the nature of patients seen in the cardiac catheterization laboratory, many are on antiplatelet therapy, and it is preferred that patients have antiplatelet therapy prior to initiation of the procedure. For these reasons we will plan on continuing antiplatelet therapy.

13.9 Hospitalization, Prolonged Hospitalization or Surgery

Any adverse event that results in hospitalization or prolonged hospitalization should be documented and reported as a serious adverse event unless specifically instructed otherwise in this protocol. Any condition responsible for surgery should be documented as an adverse event if the condition meets the criteria for an adverse event.

Neither the condition, hospitalization, prolonged hospitalization, nor surgery are reported as an adverse event in the following circumstances. Hospitalizations that do not necessitate reporting as adverse events, including those that are scheduled as a part of the study or as a part of the predetermined care of the patient, or hospitalization for preexisting conditions, including elective surgical procedures. These include:

- Hospitalization or prolonged hospitalization for diagnostic or elective surgical procedures for a preexisting condition. Surgery should not be reported as an outcome of an adverse event if the purpose of the surgery was elective or diagnostic and the outcome was uneventful.
- Hospitalization or prolonged hospitalization required to allow efficacy measurement for the study.

- Hospitalization or prolonged hospitalization for therapy of the target disease of the study, unless it is a worsening or increase in frequency of hospital admissions as judged by the clinical investigator.

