- LVEF<30%
- Decompensated congestive heart failure (CHF) or hospitalization due to CHF during the last 3 months
- Patient with a pacemaker electrode in the CS
- Mean right atrial pressure >15 mmHg
- Anomalous or abnormal CS anatomy (e.g., tortuosity, aberrant branch, persistent left superior vena cava (SVC) as demonstrated on angiogram
- CS diameter at the site of planned implantation greater than 13mm or less than 9.5 mm as measure by angiogram
- Severe chronic obstructive pulmonary disease (COPD) indicated by a forced expiratory volume in one second that is less than 55 percent of the predicted value
- Tricuspid valve replacement or repair
- Chronic renal failure (serum creatinine >2mg/dL), and or on chronic hemodialysis
- Moribund, or with comorbidities limiting life expectancy to less than one year

- Known severe reaction to required procedural medication
- Known allergy to stainless steel or nickel
- Magnetic Resonance Imaging (MRI) within 8 weeks of Reducer implantation
- Participation in another ongoing investigational trial
- Additional factors deemed unsuitable for trial enrollment per discretion of principal investigators
- Inmates

7.3 Subject Recruitment, Enrollment and Screening:

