13.1 Definitions

Unanticipated Problems Involving Risk to Subjects or Others (UPIRTSO)

Any unanticipated problem or adverse event that meets the following three criteria:

- Serious: Serious problems or events that results in significant harm, (which may be physical, psychological, financial, social, economic, or legal) or increased risk for the subject or others (including individuals who are not research subjects). These include: (1) death; (2) life threatening adverse experience; (3) hospitalization - inpatient, new, or prolonged; (4) disability/incapacity - persistent or significant; (5) birth defect/anomaly; (6) breach of confidentiality and (7) other problems, events, or new information (i.e. publications, interim findings, product labeling change) that in the opinion of the local investigator may adversely affect the rights, safety, or welfare of the subjects or others, or substantially compromise the research data, **AND**
- Unanticipated: (i.e. unexpected) problems or events are those that are not already described as potential risks in the protocol, and consent document, or not part of an underlying disease. A problem or event is "unanticipated" when it was unforeseeable at the time of its occurrence. A problem or event is "unanticipated" when it occurs at an increased frequency or at an increased severity than expected, **AND**

- Related: A problem or event is "related" if it is possibly related to the research procedures.

- Unanticipated Adverse Device Effect:

Any serious adverse effect on health or safety or any life-threatening problem or death caused by, or associated with, a device, if that effect, problem, or death was not previously identified in nature, severity, or degree of incidence in the investigational plan or application (including a supplementary plan or application), or any other unanticipated serious problem associated with a device that relates to the rights, safety, or welfare of subjects. In the event of attempted device implant with circumstances that prevent implant due to malfunction or deficiency the unused devices will be retained until arrangements for its collection are made and can be returned to Neovasc for further analysis and investigation.

There are several inherent risks associated with this protocol that must be considered. There are risks associated with the various study procedures including cardiac catheterization, CS Reducer implantation, invasive coronary reactivity testing, and exercise testing.

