13.3 Serious Adverse Event

Adverse events are classified as serious or non-serious. Serious problems/events can be well defined and include;

- Death
- Myocardial infarction
- Stroke
- Life threatening adverse procedural or periprocedural complications
- Any hospitalizations post CS Reducer implantation
- Inpatient, new, or prolonged; disability/incapacity

and/or per protocol may be problems/events that in the opinion of the sponsor-investigator may have adversely affected the rights, safety, or welfare of the subjects or others, or substantially compromised the research data. Serious adverse events are ones that may result in death or can be life-threatening, requires extended hospitalization, significant disability, meaning a substantial disruption to the person's ability to conduct normal life functions. This excludes experiences of minor medical significance such as headache, nausea, vomiting, influenza, diarrhea, accidental trauma, which may disrupt daily functions but is not substantial. Medical or scientific judgment should be exercised when deciding whether reporting is appropriate in situations.

All adverse events that do not meet any of the criteria for serious, should be regarded as non-serious adverse events.

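### Section 13.9 exempts admissions for pre-existing conditions from adverse-event classification with no worsening test, which contradicts 13.5 and 13.3

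*Combined protocol and SAP*

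**What the plan says.** Section 13.9 opens with a general rule: an adverse event that leads to or prolongs an admission is an SAE, unless the protocol gives a specific contrary instruction. It then sets out exemptions: "Neither the condition, hospitalization, prolonged hospitalization, nor surgery are reported as an adverse event in the following circumstances". The sentence that follows names two classes of admission. The first is planned stays, "including those that are scheduled as a part of the study or as a part of the predetermined care of the patient". The second is "or hospitalization for preexisting conditions, including elective surgical procedures". Three bullets come next, introduced as things the exemptions include:

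- The first concerns elective or diagnostic work: "Hospitalization or prolonged hospitalization for diagnostic or elective surgical procedures for a preexisting condition".
- The second covers stays needed for efficacy measurement.
- The third covers treatment of the target disease, and it alone carries an exception for worsening, as judged by the clinical investigator.

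Section 13.5 says that a pre-existing condition should be "recorded as an adverse event if the frequency, intensity, or the character of the condition worsens during the study period". Section 13.3 lists all admissions after Reducer implantation among serious events and states no exception.

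The opening of section 13 requires investigators to tell the sponsor-investigator of every procedure or hospitalization.

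**The concern.** Consider a participant with a known condition other than the target disease, such as heart failure, who is admitted after implantation because that condition has got worse. Section 13.5 makes this an adverse event and 13.3 makes it serious. Section 13.9, followed literally, says that neither the condition nor the admission is an adverse event. Site staff have no stated way to choose between these instructions.

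The classification matters because safety oversight runs on it. The DSMB in 13.14 is formed to review adverse events independently and to decide whether the stopping criteria are met. The 3/5 stopping rule in 13.14 and the 1-of-5 withdrawal rule in 7.4 both count serious events. In a single-arm trial of 30 patients, one event classified differently can change how the safety experience reads.

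**Working it through.** There is no figure in the plan to reproduce. The check sets the sections side by side.

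1. **Does the exemption reach a worsened condition?** The phrase in 13.9 covers admissions for pre-existing conditions in general and gives elective surgery only as one member of the class. It has no worsening qualifier. The sentence before it extends the exemption to the condition itself.

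2. **Do the bullets narrow it?** The first bullet alone would limit the exemption to elective or diagnostic procedures. But the bullets are introduced as inclusions and do not form a closed list, so the broader phrase still stands. The third bullet shows that a worsening exception was written where one was wanted, for the target disease only. Its absence elsewhere invites the reading that none applies.

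3. **Does the general rule at the start of 13.9 rescue the event?** No. That rule gives way to specific contrary instructions, and the exemption can be read as one. It also starts from an event that is already an adverse event, a status that the exemption removes. The duty in 13.10 to record all adverse events has the same starting point.

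4. **Conflict with 13.5.** Direct: the same worsened condition is an adverse event under 13.5 and not one under 13.9.

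5. **Conflict with 13.3.** Direct: its hospitalization item is unqualified and does not refer to 13.9.

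6. **Can such patients enrol?** Yes. The heart-failure exclusion in 7.2 is "Decompensated congestive heart failure (CHF) or hospitalization due to CHF during the last 3 months", with LVEF below 30% excluded separately. Compensated heart failure with an LVEF of 30% or more and no such admission in the last 3 months is therefore eligible. No criterion in 7.2 names prior arrhythmia. Section 2.3 itself says that coronary microvascular dysfunction is prevalent in patients with diastolic dysfunction and cardiomyopathies.

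7. **What is lost?** The opening of section 13 still brings the admission to the sponsor-investigator. That notice does not make the admission an adverse event, and this is a single-center trial, so the notice stays within one site. An admission classified out under 13.9 need not enter the adverse-event or SAE counts used by the DSMB and by the two rules.

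**The case against.** The strongest reply is that the sections should be read together. The first bullet points to elective or diagnostic procedures as the intended scope, 13.5 supplies the worsening test, and 13.3 makes any post-implant admission serious. On that reading an unplanned admission for heart failure or arrhythmia has a clear route to SAE status. This is probably what the authors meant. It still asks staff to give the general sections precedence over the specific exemption, and nothing in the protocol says so.

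Two further replies limit the consequences, and both stand in part. The 3/5 rule counts only events deemed secondary to the device, and an admission judged device-caused would be hard to describe as simply one for a pre-existing condition. That relies on the causality judgement being made, though, and an event already classified out may never reach it. Second, the prespecified safety endpoint in 6.3 is procedural MACE: death, myocardial infarction, CS perforation, CS occlusion or urgent dilatation. None of these depends on how an admission is classified, so that endpoint is unaffected. The adverse-event and SAE tabulations are not protected in the same way.

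A reader might also infer that an implant stay extended by a complication is exempt, because 13.9 mentions both prolonged stays and study-scheduled admissions. The text does not support this. Such an extension is neither scheduled nor needed for efficacy measurement, so the first sentence of 13.9 still makes it an SAE. Nor is 13.1 contradicted. Its words "hospitalization - inpatient, new, or prolonged" are one element of seriousness in the definition of an unanticipated problem, which must also be unanticipated and related.

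**Conclusion.** The contradiction is real and the text is wrong as written. Section 13.9 exempts admissions for pre-existing conditions without a worsening test, against 13.5 and against the unqualified item in 13.3. The conclusion assumes that staff could follow 13.9 literally, and that some enrolled patients have a relevant prior condition.

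The risk is loss of AE or SAE classification. A reader might go further and infer that such admissions go unreported altogether; the notification duty at the opening of section 13 rules that out.

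The number of events affected cannot be estimated from the documents. It is tempting to use the arrhythmia row of Table 1. The two studies give (1 + 4)/(52 + 204) = 5/256 = 2.0%, or 30 × 5/256 = 0.59 expected patients. At the REDUCER-I rate of 4/204, the chance of at least one in 30 is 1 − (1 − 4/204)^30 = 45%. Adding the commercial-use column (0/1840) gives 5/2096 = 0.24%, or 30 × 5/2096 = 0.07 expected. Neither figure measures lost events. Table 1 does not say whether any of these arrhythmias led to admission or arose in a patient with a prior arrhythmia, and the share of eligible patients with such a history is not given. Pulmonary edema, the entry closest to the heart-failure example, has no events in any column.

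**What to change.** In 13.9, limit the pre-existing-condition exemption to elective, diagnostic or pre-planned admissions for a condition that has not worsened by the 13.5 test. In 13.3, state that the hospitalization item is subject only to the 13.9 exemptions as limited in this way. The three sections would then give one answer for the same admission.

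The cost is one or two sentences of protocol text and possibly a few more reported SAEs. No procedure, visit or sample-size change follows from it.

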13.10 Recording of Adverse Events

At each contact with the subject, the study team must seek information on adverse events by specific questioning and, as appropriate, by examination. Information on all adverse events should be recorded immediately in the source document, and also in the appropriate adverse event section of the case report form (CRF) or in a separate adverse event worksheet. All clearly related signs, symptoms, and abnormal diagnostic, laboratory or procedure results should be recorded in the source document.

All adverse events occurring during the study period must be recorded. The clinical course of each event should be followed until resolution, stabilization, or until it has been ultimately determined that the study device or participation is not the probable cause. Serious adverse events that are still ongoing at the end of the study period must be followed up, to determine the final outcome. Any serious adverse event that occurs after the study period and is considered to be at least possibly related to the study treatment or study participation should be recorded and reported immediately.

13.11 Reporting of Serious Adverse Events and Unanticipated Problems

When an adverse event has been identified, the study team will take appropriate action necessary to protect the study participant and then complete the Study Adverse Event Worksheet and log. The sponsor-investigator will evaluate the event and determine the necessary follow-up and reporting required.

13.12 Sponsor-Investigator reporting: notifying the Mayo IRB

The sponsor-investigator will report to the Mayo IRB any UPIRTSOs and Non-UPIRTSOs according to the Mayo IRB Policy and Procedures. All serious adverse events must be reported in writing to both the Institutional Review Board by the investigator himself as institutional policies mandate. The investigator must then provide a summary describing the SAE in detail and his assessment of how related the event is to the study device. The documentation related to the SAE must follow the initial SAE report immediately as available. As new information becomes available to the investigator, the investigator must continue to collect and forward this information, and provide a corresponding follow-up summary.

Information collected on the adverse event worksheet (*and entered in the research database*):

- Subject's name:
- Medical record number:
- Disease/histology (if applicable):
- The date the adverse event occurred:
- Description of the adverse event:
- Relationship of the adverse event to the research (device, procedure):
- If the adverse event was expected:
- The severity of the adverse event: (use a table to define severity scale 1-5)
- If any intervention was necessary:
- Resolution: (was the incident resolved spontaneously, or after discontinuing treatment)
- Date of Resolution:

The sponsor-investigator will review all adverse event reports to determine if specific reports need to be made to the IRB and FDA. The sponsor-investigator will sign and date the adverse event report when it is reviewed. For this protocol, only directly related SAEs/UPIRTSOs will be reported to the IRB.

13.13 Sponsor-Investigator reporting: Notifying the FDA

The sponsor-investigator will report to the FDA any unanticipated adverse device events and the reviewing IRB as well as all participating investigators within 10 working days after the Sponsor-Investigator is aware of the occurrence.

The sponsor-investigator will submit annual progress reports to FDA which will include a summary of progress to date, a summary of results, a summary of anticipated and unanticipated adverse effects, any deviation from the protocol, any minor change to the protocol, and any changes to the risk analysis. State any future plans including any anticipated changes to the investigation and include any resulting publications from the study.

Any clinically important increase in the rate of serious suspected adverse reactions over those listed in the protocol or product insert will be reported as a serious suspected adverse reaction. This will be reported to both the Institutional Review Board by the investigator himself as institutional policies mandate after the sponsor-investigator's initial receipt of the information about the event.

13.14 Stopping Rules

The principal investigator will review all serious adverse events and be involved in the decision to stop the study. The study will be stopped if 3/5 patients experience serious adverse events deemed secondary to the study device, including death, cardiovascular mortality, bleeding, stroke or sepsis thought to be secondary to CS Reducer implantation. Given that the CS Reducer has no FDA approved indication yet, and to ensure independent review and reporting of adverse events and determine if study stopping criteria have been met, a DSMB committee will be formed. The committee will be formed of 3 independent members: [name], an independent interventional and structural heart disease expert will be a member and chair the committee, and the remaining 2 members will be an independent cardiologist who evaluates and manages patients with coronary microvascular dysfunction at Mayo Chest Pain Clinic, and an independent Mayo Clinic statistician. These members will be named prior to initiation of the study.

